3. Description of use of the PDMP and study-associated BPAs, specifically monitoring
 - # of times PDMP activity/website is checked by site/practice/service, monthly, and specialty
 - Frequency of use of the PDMP one-click button per visit and per opioid prescription
 - Frequency of CDS and BPA trigger overall and per opioid prescription
 - Frequency of prescriptions for which the BPA would have fired but the prescriber had already checked the PDMP (look for change over time – do the BPAs lead to learning & change in prescriber behavior)
 - Number of times CDS alert fired, total and per visit (the alert is designed to only fire once during any encounter, thus the per visit rate will be <1)
 - Reviewed (via radio button or via alert)/unable to review/blank

- Resulted in signed Rx (reviewed/unable checked, signed prescription)
- Use of training tools and website. Identifying information on individuals accessing tools will not be recorded.
- Qualitative/semi-quantitative feedback from users as the CDS alerts are implemented

Patient specific measures will include:

- Number of controlled medication prescriptions, both within UCHealth and outside, based on PDMP data (including prescription details to include generic name, dosage, MMEs, days prescribed)
- Use of the PDMP by the prescriber prior to each controlled medication prescription written
- NarxCare risk score at the time of each prescription
- Number of providers/practices used for controlled substance prescriptions
- Number of pharmacies used for controlled substance prescriptions
- Diagnosis of any substance use disorder after the index visit date
- Accidental overdose of controlled substance after the index date (if data available)
- Patient demographics and clinical history characteristics

Educational outreach analysis: Alert firings for providers part of the educational outreach group will be analyzed for percent of non-compliant firings before outreach vs after as well as a comparison between the two different educational outreach efforts (email or EHR messaging system). Non-compliance is defined as 3 or more alerts for a single patient/encounter or >80% of firings closed using the comment/close option rather than using the PDMP link. Firings over time will be tracked as will changes in compliance before and after each outreach attempt. These data will be de-identified prior to reporting. Data will be examined for patterns based on demographics or work environment.

Calculation of sample size:

The number of providers who choose to provide input on CDS design and implementation can only be very roughly estimated. The UCHealth system includes approximately 18,000 individual prescribers, not all of whom will see the alerts. Assuming 5% of individual prescribers choose to provide feedback through the survey available on the website, approximately 900 providers could provide feedback. No minimal response rate is required for significance as no hypotheses will be tested with these data. Survey data will be summarized via descriptive statistics only.

The driving factor in total enrollment is the patient outcome phase. As the tools will be active over the course of approximately 20 months, total patient counts over 20 months, rather than a power calculation, inform our assumptions about enrollment. Of the approximately 2.3 million individuals in the UCHealth system between the ages of 12 – 89, approximately 290,000 received at least one opioid prescription in the last 20 months. Approximately 906,000 individual patients were seen in the UCHealth system in the same time period.

The CDS tools used in this study will automatically query each patient record in order to obtain risk data, but data will only be seen by a provider in a fraction of cases. Based on the advice of privacy officials and COMIRB staff during the design of this study, all individuals queried are included as study participants, even if a provider does not see a study associated CDS alert for all

patients. As such, it is estimated that 950,000 patients will be included in this study. The number of patients queried will be monitored during the course of the study and updated as needed.

Data to be collected:

Variable	Definition	Importance
Prescriber/system data		
Overall controlled medication prescribing rate	Total number of opioid/sedative/stimulant prescriptions divided by total number of visits at each site and the hospital system	Measures the overall impact for each CDS tool
Individual provider controlled medication prescribing rates	Total number of opioid/sedative/stimulant prescriptions divided by total number of encounters for each provider	Measures the behavior and practice variation of individual prescribers for each CDS tool
Overall rate of PDMP use	Total number of times PDMP is accessed when opioid/sedative/stimulant prescriptions are written	Measures how readily providers obtain information for each CDS tool
Provider specific rate of PDMP use	Total number PDMP searches for each provider, changes over time for each provider	Measures provider search behavior and variability changes for each CDS tool
Overall prescription rate after accessing PDMP	Number of times opioid/sedative/stimulant were prescribed after accessing the PDMP	Evaluate the impact of PDMP review on the decision to prescribe controlled medications
Provider demographics	Age, sex (M/F), years of employment (when available, data saved in EHR)	Evaluate variability in provider acceptance based on information stored in the EHR system.
Provider specific prescription rate after accessing PDMP	Total number of opioid/sedative/stimulant prescriptions divided by the number of times the provider accessed the PDMP for each provider	Evaluate provider variability in interpretation with and without decision support
Patient specific outcomes		
Patient demographics	Age, gender, ethnicity, insurance type	Description of patient population
Visit characteristics	Date of service [#] , service location, provider specialty, zip code	Evaluate visit for possible influences on patient and provider outcomes

Opioid prescription	Type, name, strength, number of pills, prescriber	Evaluate the effectiveness of the CDS tools
PDMP search completed	Yes/no	Evaluate the effectiveness of the CDS tools
Patient characteristics	Discharge diagnosis, past medical history, current co-morbid diagnoses, social history, other medications	Evaluate patient variability and other influences on prescribing/risk levels
CDS activation	Activation of CDS alert, which alert	Identify risk factors for patient as presented to prescriber
Prescriptions from PDMP	Type of medication (opioid, sedative, stimulant), date written [#] , date filled, [#] medication name, strength, formulation, # of pills prescribed, # of days supply, milligram morphine equivalents (MME), insurance type, pharmacy number	Evaluate patient outcome, needed for complete picture of prescription use
Non-UCHealth visits from All Payers Claims Data	ED visits, hospitalizations	Evaluate overall patient outcome, including unintended consequences of limitation of prescription pain medications
Provider Feedback		
Use of training materials and website	Usage (file access) over time	Measure of effectiveness of educational efforts
Survey responses	See draft included with submission	Provide ideas of aspects of CDS tool considered worthwhile by users. Descriptive statistics only, non-quantitative analysis.

[#]All data will be deidentified prior to release of data to the research team.

G. Summarize Knowledge to be Gained:

As PDMP use improves prescribing decisions, this study will provide immediate, direct benefit to study participants. Further, it will provide greater understanding of the reasons why clinicians use or do not use the PDMP as recommended, and explore several options for improving utilization and maximizing appropriate clinician use of the information provided. Finally, it will explore patient focused outcomes when the PDMP is used (or not), and if patient outcomes are better (defined as less aberrant or long term opioid use) when PDMP CDS tools are better integrated into the provider's workflow and better focused on providing high impact, risk based information

to the provider at the appropriate time. Given the number of patients and providers covered by the UCHealth system, and the geographic dispersion of UCHealth facilities around the state, it is likely that results will be generalizable through the state and other states through the region. The degree to which our findings will be generalizable beyond Colorado and the mountain west regions is uncertain.

H. References:

- [5] Vestal C. Overdose Deaths Fall in 14 States, Vol. 2019: Pew Trust, 2018.
- [6] Ingalls J. More than 1,000 Coloradans Lost to Drug Overdoses in 2017, Vol. 2019: Colorado Health Institute, 2018.

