issue, the current study will focus on designing, testing and implementing CDS tools to ensure delivery of the right PDMP information to prescribers at the right time within their workflow to increase compliance with the recommended best practice of PDMP review.

IV. Research Methods

A. Outcome Measure(s):

Primary outcome:

- Changes in the percentage of high-risk patients (patients who are flagged by the CDS logic) who are checked in the PDMP

Secondary outcomes:

- Changes in the percentage of high-risk patients (patients who are flagged by the CDS logic) who receive a controlled medication prescription
- Overall utilization of the PDMP prior to prescribing for low risk/naïve patients vs. high risk patients
- Percentage of patients who receive a controlled medication prescription who go on to long- term or aberrant use of controlled medication when CDS is used vs. controls

B. Description of Population to be Enrolled:

Two distinct populations will be involved in this study.

1. Health care providers licensed to prescribe opioid analgesics in the UCHealth system. These individuals will use CDS tools provided in the course of normal clinical care and have the opportunity for qualitative feedback on tools. We will collect de-identified data on CDS use and prescribing practices of providers. There will be no attempts to link qualitative responses with measures of prescribing practices, which will be measured system wide as described elsewhere. Oncology, hospice/palliative care, and pediatric practices will be excluded

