2. Patients seeking care in the UCHealth system, who may receive an opioid prescription. The population will be limited to non-prisoners 12-89 years of age. Individuals with an active cancer diagnosis, sickle cell disease, or receiving specific end of life care are excluded. Pregnant women and decisionally challenged people will be included but are not considered a target population. No efforts will be made to include these individuals. Patients with limited literacy or limited English fluency will be included but are not considered a target population. Juveniles seen at providers included in the specialties of interest will be included (ages 12-17 inclusive) due to the inclusion of their health care provider. On the advice of pediatric toxicology experts, a cut point of 12 years of age is a clinically relevant age at which misuse of opioid analgesics and other controlled medications becomes a notable risk. However, no efforts will be made to target or enhance inclusion of juveniles. Pediatrics-only specialist offices will not be included in rollout of the CDS tools. Outcomes measures from juveniles will be examined separately from adults but may be included in the overall population if statistically appropriate.

C. Study Design and Research Methods

This will be a 1) cluster-randomized (by practice, as identified by a group of providers who work in the same department or set of departments within UCHealth) study for ambulatory/outpatient providers and 2) a randomized study (by provider) for emergency medicine and inpatient providers, with four study arms:

1. Arm 1: No change in practice
 - Providers are free to access the PDMP when prescribing via the existing integrated PDMP button.
 - This control group will enable monitoring of the secular changes in rates of controlled medication prescription within the UCHealth system.
 - In order to facilitate analysis of patient outcomes, CDS logic as in group 4 will run “silently” in this group such that risks are identified and recorded but not seen by the provider.
2. Arm 2: “Mandatory” use of the PDMP for all opioid prescriptions.
 - A best practice alert (BPA) will be triggered and fire when ordering an opioid prescription. The BPA will not appear (i.e. it will be suppressed) if the provider already reviewed the PDMP within the encounter. The BPA is shown in Figure 2 below.

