 - Although this condition is termed “mandatory” use, it is not a hard stop. The provider can easily close the window without consulting the PDMP and the prescription can be signed whether the PDMP has been consulted or not. The BPA will be built to track utilization of the BPA vs. bypass. Note: This has been deemed too interruptive for

[figure not shown]

Figure 2: Example BPA used in prior study.

ambulatory clinics and they will not be included in this arm.

3. Arm 3: CDS for high risk patients based on PDMP data
 - Based on initial interviews with providers (see 19-3063) CDS support will be designed to be supportive of provider workflows via interruptive alerts (BPAs) for high-risk patients only. No alerts will fire for patients without high risk indicators based on data in the PDMP or prescription history as shown in Epic. An example is given below. Exact phrasing may be modified during final testing in order to streamline appearance of the alert.
 - Again, BPA will be triggered upon entry of an opioid or benzodiazepine prescription and will fire only for patients determined to be at risk for controlled medication associated adverse events, misuse or overdose, based on logic built to identify high-risk characteristics. Definition of these risk characteristics is based on CDC guidelines and include: NarxCare opioid or overall overdose risk score (PDMP based) indicating the patient is in the highest ~5% of the population for controlled medication risk, initiating opioid treatment with an extended or long acting release formulation with no opioid usage in the previous 100 days, or information in the PDMP or EHR indicating overlapping opioid use or co-prescribing of a sedative with an opioid.
 - One-click access to the PDMP for all patients will be maintained as in other arms. If the provider reviews the PDMP during the encounter before prescribing, the BPA will be suppressed.

- As in Group 2, this is not a truly mandatory check and can be bypassed. BPA messaging was determined based on work with providers to deliver the most useful and clear information.
- The text displayed in the alert will be specific to the patient. BPA logic and phrasing is included in Appendix A.

[figure not shown]

Figure 3: Sample alert.

4. Arm 4: CDS for high risk patients based on PDMP and/or clinical characteristics

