In addition, a second silent alert (3rd level in model) will fire for all eligible patients seen by study providers, using the same criteria as the PDMP + EHR alert described above. As with the previously described alert, PDMP use will not suppress this alert so that all patients can be captured. This alert will allow us to document the same risk information for all study patients so we can describe patient risk information across intervention groups. Much of this information tends to be transient and variable over time. Having a snapshot of the data at that moment will be valuable in the final analysis.

Intervention→ Purpose ↓	Provider Group 1: Control (no alert)	Provider Group 2: "Mandated"	Provider Group 3: PDMP	Provider Group 4 [CN1] PDMP + EHR
1 st level: Visible alert		
VISIBLE 14118
 
 Trigger: controlled rx PDMP attestation suppresses: yes 	
VISIBLE 14643
 
 Trigger: controlled rx, + PDMP criteria PDMP attestation suppresses: yes 	
VISIBLE 14644
 
 Trigger: controlled rx, + PDMP and/or + EHR PDMP attestation suppresses: yes
2 nd level: Capture all PDMP use (silent)		
SILENT
 
 Trigger: Mirror of 14118 PDMP attestation suppresses: No 	
SILENT
 
 Trigger: Mirror of 14643 PDMP attestation suppresses: no 	
3 rd level: Capture full patient risk profile (silent)	
SILENT
 
 Trigger: Mirror of 14644 PDMP attestation suppresses: no 	
SILENT
 
 Trigger: Mirror of 14644 PDMP attestation suppresses: no 	
SILENT
 
 Trigger: Mirror of 14644 PDMP attestation suppresses: no 	
SILENT
 
 Trigger: Mirror of 14644 PDMP attestation suppresses: no

Figure 4: Visible (top row) and silent alerts used in the study CDS

Due to primary care not allowing interruptive BPAs, there will be two units of randomization corresponding to the ED/hospital discharge and the outpatient care setting, respectively.

Prescribers working in UCHealth Emergency Departments and inpatient facilities

- Each ED/inpatient prescriber will be randomized to one of the four study arms described above. Dentists will be excluded.

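### The plan describes the trigger of the high-risk flag in two ways; if the flag needs an order, the Hypothesis 2 outcome misses prescribing avoided before order entry

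*Combined protocol and SAP*

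**What the plan says.** Hypothesis 2 (section I) predicts that a focused CDS tool lowers the percentage of high-risk patients who receive a controlled prescription. Section IV.A makes this a secondary outcome: "Changes in the percentage of high-risk patients (patients who are flagged by the CDS logic) who receive a controlled medication prescription". The primary outcome rests on the same definition: "Changes in the percentage of high-risk patients (patients who are flagged by the CDS logic) who are checked in the PDMP". Neither entry states which alert level supplies the flag, whether the unit is a patient, encounter or order, or over what period a prescription counts.

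Section IV.C describes the alerts:

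- **Visible alert, Arm 3 text:** "BPA will be triggered upon entry of an opioid or benzodiazepine prescription and will fire only for patients determined to be at risk".
- **Visible alert 14644, Arm 4, in Figure 4:** "Trigger: controlled rx, + PDMP and/or + EHR".
- **Third-level silent alert in Figure 4, the only one drawn in all four arms:** "Trigger: Mirror of 14644". The one stated change of setting is that PDMP attestation does not suppress it.
- **The same silent alert in the paragraph before Figure 4:** it fires for every eligible patient whom a study provider sees, on the PDMP + EHR criteria, so that the same risk information is held for all study patients. No order is mentioned.

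The Arm 3 risk criteria include "initiating opioid treatment with an extended or long acting release formulation with no opioid usage in the previous 100 days", as well as overlapping opioid use and co-prescribing of a sedative with an opioid. For the detailed logic the protocol says "BPA logic and phrasing is included in Appendix A". That appendix is not in the supplied text.

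**The concern.** The denominator should be fixed by something the intervention cannot alter. If the common flag needs a controlled order, a high-risk patient for whom the provider decides not to order anything is in neither numerator nor denominator, and that decision is the behaviour Hypothesis 2 hopes to produce. The denominator also becomes an event after randomisation that the alerts may change, so the arms may be compared on differently selected sets of patients.

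The protocol makes avoidance before order entry plausible. Section IV.C allows the PDMP check to be attested before a prescription is entered. Sections IV.C and IV.F plan to look for learned changes in providers' PDMP use over time. Section III reports that the odds of an opioid prescription fell with each prior fill when the PDMP was searched (OR 0.92) but not otherwise (OR 1.01), although that comparison does not show whether the decision came before or after order entry.

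At stake is one of the two stated hypotheses. The primary outcome's denominator carries the same ambiguity.

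**Working it through.** The plan states no power, effect size, order-entry rate or signing rate for Hypothesis 2, so there is no figure to reproduce. The check compares the two readings.

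**1. What each reading measures.** Let q be the share of risk-positive patients seen for whom an order is entered, and s the share of those orders signed. If prescriptions are counted at the flagged encounter:

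- order-entry flag: outcome = s
- flag on all eligible patients seen: outcome = q × s

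The only related figures in the plan are in section IV.F: about 290,000 patients with an opioid prescription and 906,000 patients seen over 20 months, and 290,000 / 906,000 = 0.32. This covers all patients and opioids only. It shows that the two denominators could differ widely, but does not estimate q for high-risk patients.

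**2. How much of a true effect is shown (assumed values).** Let r be the true relative fall in high-risk prescribing, f the fraction of that avoidance occurring before order entry, and a the share of entered control orders abandoned. Orders avoided before entry are assumed to have otherwise been signed at the control rate.

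- control outcome = 1 − a
- treated outcome = (1 − a)(1 − r) / (1 − f·r)
- relative fall shown = r(1 − f) / (1 − f·r), since a and the baseline prescribing rate cancel

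| f | r = 0.25 | r = 0.10 |
|---|---|---|
| 0 | 25.0% | 10.0% |
| 0.25 | 20.0% | 7.7% |
| 0.50 | 14.3% | 5.3% |
| 0.75 | 7.7% | 2.7% |
| 1 | 0% | 0% |

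Count check: take 1,000 high-risk encounters, 40% signed in control, a = 0.05, r = 0.25, f = 0.5. Control: 400 / 0.95 = 421.1 orders, and 400 / 421.1 = 0.950. Treated: 421.1 × (1 − 0.125) = 368.4 orders, and 300 / 368.4 = 0.814. The relative fall shown is 1 − 0.814 / 0.950 = 0.143, against a true fall from 40% to 30%, which is 0.25.

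**3. The opposite case.** Assume q between 0.32 and 0.60 and control s between 0.90 and 0.99.

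- If the tool cuts ordering by 10% before entry, the order-entry outcome moves 0.0 points and the all-patients outcome falls by 0.10 × q × s, which is 2.9 to 5.9 points.
- If it cuts signing by 10% after the alert, the order-entry outcome falls by 0.10 × s, which is 9.0 to 9.9 points, and the all-patients outcome again falls 2.9 to 5.9 points.

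The order-entry version is therefore not always the less responsive one. It responds to one of the two pathways only.

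**4. The wider reading.** Suppose the silent flag fires for every eligible patient seen. Starting treatment with a long-acting opioid can still be met only through the new order. Overlapping opioid use and sedative co-prescribing may also depend on it, and the supplied text does not say. Patients flagged only by such a criterion are in the denominator because of the prescription then counted in the numerator.

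**The case against.** The strongest reply is that the description written specifically for the third-level flag is the broad one, while the Figure 4 cell is shorthand in a row labelled as capturing the full risk profile. Section IV.F adds that the tools query each patient's record and expects 950,000 participants, far more than the 290,000 with an opioid prescription. The Arm 3 order-entry trigger and the suppression rule concern visible alerts. The validation step, which confirms that a controlled medication was prescribed, names no alert level. Appendix A may settle the matter. This has weight: the harmful reading is not established. But a record query is not a flag firing, the paragraph's reference to the same criteria and to eligible patients can be read consistently with Figure 4, and nothing supplied says which version defines the outcome.

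A reader might cite the Arm 1 text, "such that risks are identified and recorded but not seen by the provider", as proof of a wider flag. It is not: that sentence runs the Arm 4 logic silently, which may include the order trigger.

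It is also fair that a visible alert acts at order entry, so its direct effect follows entry and would be captured. Avoidance before entry needs learned behaviour or outreach. The per-visit and per-encounter prescribing rates in section IV.F would register some avoided orders, but they are not restricted to high-risk patients and are not the Hypothesis 2 outcome.

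**Conclusion.** The point holds as a conditional one and should be fixed; confidence is medium. Figure 4 and the paragraph before it describe the common flag differently, and the supplied text does not say which defines high-risk. If Figure 4 governs, the outcome is conditioned on an order being entered, mainly reflects orders abandoned after entry, and has a denominator the intervention can change. If the paragraph governs, most of the problem goes, but the order-dependent criteria remain.

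The size is unknown. The table rests wholly on assumed values and runs from the full effect (all avoidance after the alert) to none (all of it before entry), so it shows direction and range only.

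Two stronger readings are not supported. A reader might infer that the outcome simply is the signed share of flagged orders. Section IV.A counts patients and states no window, so a patient could also receive a different or later prescription. A reader might also infer that the trial will miss a real effect on prescribing. That would need Figure 4 to govern and most avoidance to precede entry, and the documents show neither.

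**What to change.** - Reconcile Figure 4's third-level trigger with the paragraph before it. State which flag, unit and prescription window define the Hypothesis 2 outcome.
- Analyse Hypothesis 2 among all eligible encounters with randomised providers or practices for patients meeting risk criteria that do not depend on the new order, applied identically in all arms.
- If the silent flag fires without an order, use it, leaving out patients flagged only by an order-dependent criterion. List those criteria explicitly.
- If it does not, build the denominator in the planned retrospective extract from EHR history and PDMP fills dated before the encounter, with NarxCare only where it is recorded independently of an order.
- Report the signed share of flagged orders separately as a process measure, using the signed-prescription field already listed among the BPA measures in section IV.F.
- State whether the primary outcome uses the same denominator.
- Leave the alert logic unchanged, as section IV.F requires.

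**Cost.** If the silent flag already fires without an order, this is a few sentences of analysis text. Otherwise the retrospective query must also include high-risk encounters without an order, using data sources already planned. The downside is that order-dependent criteria drop out, and so does NarxCare where it is captured only at each prescription (the patient measures in section IV.F), although section II says those scores drive activations. The system-wide scores collected during validation are deliberately unlinked and cannot fill the gap. The fallback population would therefore differ from the alert-firing one, and the report should say so.
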